1) Control: Very brief advice and follow-up. The practice nurse will provide brief structured advice (less then 5 minutes) about a healthy diet (healthy food swaps) and physical activity (advice to take 30 minutes of moderate intensity exercise per day) using brief written materials. For follow-up, nurses will arrange very brief follow-up (5 minute appointment) with sufficient time for measurement of weight only at 6 months and 12 months. Nurses will not have time to perform counselling, and will also actively be instructed to provide supportive comments only and not to engage in active behavioural intervention over and above the brief structured advice.

- **2) Web intervention with nurse support**. The aim in this group is to provide a more intensive evidence-based intervention, but which should require less than half the time of traditional face to face evidence-based lifestyle interventions. The intervention components are as follows:
 - Physical activity. Diet and physical activity targets supported by drug treatment as necessary are based on NICE guidance. Participants will be given targets of at least 2.5 hours of moderate intensity physical activity per week (brisk walking), and, where walking is the preferred physical activity, will be encouraged, where possible, to aim for at least 10,000 steps per day supported by pedometers⁴⁰. Observational studies suggesting 1500-2000 Kcal per week may be required to maintain weight loss and thus a flexible approach will be used to increase the target amount of physical activity if necessary⁷.
 - Diet. Participants will be given the choice of either low calorie or low carbohydrate approaches (based on a strong preference expressed in the pilot phase by patients for a choice of dietary approaches). These eating plans are intended to achieve a sustainable rate of weight loss of 0.5-1Kg a week ¹⁷; a graded approach to negotiating more demanding dietary targets will be used if no weight loss is occurring. Patients who have succeeded in losing 5% of body weight will be given the choice of continuing to pursue gradual weight loss or attempting to maintain this weight loss.

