
- reinforced by pedometer use⁸, or setting personal physical activity goals. The patient can select all subsequent weight loss sessions from a menu which includes coverage of healthy drinking patterns, relapse prevention, and coping with cravings, stress-induced eating, busy times and social pressures.
- Nurse support. Very brief appointments for weight measurement at 6 months and 12 months (final follow-up) will occur as in the control group. In addition all patients will be offered brief face to face behavioural assessments at 2 weeks, 6 weeks, and 3 months. If a rate of weight loss equivalent to 5% weight loss over 6 months is not being achieved or maintained which we anticipate could be up to half the cohort face to face appointments will be made, up to a maximum of 4 more appointments in total in the first year (which is half the number of the average face to face appointments for dietary and behavioural counselling from trials documented in the NICE review⁵). In line with NICE guidance⁵ if 5% weight loss in not achieved Orlistat will be offered; it will be stopped according to standard stopping rules ⁵. Orlistat can also be used for weight maintenance⁵. The purpose of the nurse contacts is to provide reinforcement, and also to be able to help patients address ongoing or new issues where the web has provided limited support. Where issues arise the approach will be to encourage patients to find their own solutions to the problems raised.
- Other features. Based on previous evidence from systematic review of particular strategies to encourage maintenance of weight loss¹¹, patients will asked to participate in web based peer interaction, and to involve the family or spouse to help limit weight regain.

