- **3) Web intervention with minimal face to face support.** This group aims to provide a very brief intervention with minimal face to face contact time which therefore could be applied more rapidly and extensively in the NHS. Patients will work through the website, will be prompted to use it regularly by email, and brief face to face contact for weighing only at 6 and 12 months as in the control group. In addition this group will have a brief (10 min) face to face consultation at 2 weeks to confirm the physical activity and dietary targets, 3 brief online contacts at 1, 2, and 3 months and up to 2 further telephone contacts (i.e. 3 brief additional personal contacts compared with the control group until final follow-up) for patients not losing 5% of weight.

Support and training for Nurses. We have shown in piloting that nurses can learn to use the structured intervention materials both easily (i.e. requiring relatively little training) and effectively. The web pages for nurses a) provide a brief overview of the rationale, philosophy and structure of the intervention, b) provide a structured guide to the content of each patient support session c) give nurses access to an overview of their patients' progress and the content of each session, and d) send email reminders and notifications to nurses when patient support sessions are required (at timed intervals and if patient not using website or not losing weight), and include a tick-box record for nurses to complete logging what support has been provided.

Proposed time period for retention of relevant trial documentation

Trial documentation will be kept for 15 years.

Proposed outcomes/data collection (at baseline and unless specified at 6 and 12 months). Primary outcome measure:

Weight (primary outcome): lightly clothed, without shoes, at the same time each day, and using automated Tanita digital scales (which will also allow measurement of body composition).

Secondary outcome measures:

Food and drink consumption and physical activity (at baseline and final follow-up): These behavioural measures (and intentions/attitudes to behaviour – see below) will be made in the intervention group at baseline and follow-up but in the control group only at final follow-up to avoid

such measurement being a prompt for behaviour change in the control group.

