Adherence and predictors of adherence. We will measure intention to change behaviour for each specific behaviour, and other items based on components of the TPB⁵⁶ (attitudes, social norms, perceived behavioural control) ^{2;15;16} ⁵⁶. We will measure behavioural adherence through self report which is likely to strongly predict weight loss³⁵. All website usage is automatically recorded, including frequency and duration of logins, options selected and all data inputted (e.g. weekly goal achievement).

Outcome measurement: At the appointments with the practice nurse (baseline, 6 months, 12 months), the physiological measurements will be performed, and patients weighed; research staff blind to group will also perform a final weight measurement at 12 months. For the few patients who do not provide questionnaire answers we will perform up to 2 emails/mailings, and telephone follow-up of those still not responding.

Socio-Demographic data. Age, gender, education, internet experience, social deprivation indices based on post code will be recorded.

Notes review. All patient's notes will be reviewed to document consultations, returns, time to return, reasons for returns, complications, economic data and any subsequent referrals. ⁵⁷

Sample size. We wish to compare each of the intervention groups primarily with control but also with each other so for our primary outcome (weight) we allow for alpha=0.017 (i.e. 0.05/3) to minimise type I error. For a standardised effect size of 0.33 (i.e. a small effect size, equivalent to 2-3 Kg difference assuming an SD of change of 6.5-7.5 Kg^{6,48}) and 80% power this requires 174 patients per group with complete data, or 654 patients in total allowing for 20% loss to follow-up (hence we will aim to recruit a minimum of 660 patients).

Analyses

Primary analysis: Repeated measures ANOVA for the principal continuous outcomes (i.e. weight) between groups and for the secondary outcomes, controlling for stratification variables.

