Since the study will use recommended strategies there should be no risk to participants. Major complications are unlikely in this sample. Given the structured advice to patients – probably better information than is normally available in routine care - the standard of care in the control group is likely to be higher than routine practice since most patients with obesity currently get little or no help either in weight loss or weight maintenance.

Project timetable.

0-12 months secure local approvals; approach recruit and train practices; prepare practices for recruitment including preparing list of patient and letters; perform ongoing qualitative work with existing pilot sample; pilot the website to address maintenance.

12 months - 18 months recruit patients for main trial

18 to 30 months follow-up patients from main trial

30 to 36 months complete data collection, cleaning, analysis and report writing

Reference List

- (5) Obesity guideline development group. National Institute for Health and Clinical Excellence: Obesity full guideline. Nice org 2006; http://guidance.nice.org.uk/CG43/guidance.

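### Complications are captured only from practice notes, while scheduled practice contacts differ by arm, so any between-arm comparison of complications risks unequal ascertainment

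*Protocol*

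**What the plan says.** Under Notes review, within the outcomes and data collection part of the protocol: "All patient's notes will be reviewed to document consultations, returns, time to return, reasons for returns, complications, economic data and any subsequent referrals". No other way of collecting complications is described. The section on risks and benefits expects few: "Major complications are unlikely in this sample".

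The contact schedules are under Planned interventions:

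- Control: a five-minute nurse appointment "with sufficient time for measurement of weight only at 6 months and 12 months".
- Web with nurse support: the same two appointments, and in addition "all patients will be offered brief face to face behavioural assessments at 2 weeks, 6 weeks, and 3 months". Patients not reaching or keeping the intended rate of weight loss, anticipated to be as many as half, may have "up to a maximum of 4 more appointments in total in the first year".
- Web with minimal support: the same two appointments, and "this group will have a brief (10 min) face to face consultation at 2 weeks". There are also three online contacts and up to two telephone contacts.

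The recruitment and participation outline lets either the practice or the research team complete the notes review, and states no blinding for it.

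**The concern.** A complication enters the trial data only if someone at the practice writes it down. Each scheduled contact is an occasion for a patient to mention a problem and for a nurse to record it, and the number of such occasions is part of what distinguishes the arms. With identical true rates of complications, the notes could still show more in the web arms, most of all with nurse support.

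The web arms also carry exposures that the control description lacks: a low-carbohydrate eating plan through the website and, under nurse support, an offer of Orlistat. A reader will want to know whether these caused problems. An excess in the web arms could be real or could come from recording, and the data would not tell the two apart. An analysis plan could not repair this later, because it cannot supply evenly collected complication data that were never gathered.

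A smaller matter sits in the same sentence. Return is not defined, and nothing says whether scheduled trial visits count among consultations and returns.

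**Working it through.** The protocol gives no figure for this point, so there is none to reproduce. The check is a count of contacts, followed by illustrations whose inputs are assumptions.

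**1. Scheduled contacts after baseline, to 12 months**

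| Arm | Calculation | Total |
|---|---|---|
| Control | 6 and 12 months | 2 |
| Minimal support, face to face | 2 weeks + 6 and 12 months | 3 |
| Minimal support, with telephone | 3 + up to 2 | up to 5 (3 online contacts not counted) |
| Nurse support, offered to all | 2 weeks, 6 weeks, 3 months + 6 and 12 months | 5 |
| Nurse support, maximum | 5 + 4 | 9 |

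If half of the nurse-support arm used all four extra appointments, its mean would be 5 + 0.5 × 4 = 7.

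**2. Ratio of recording opportunities to control**

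On trial contacts alone, nurse support against control is 5/2 = 2.5 to 9/2 = 4.5. Practice notes also hold ordinary attendances. With *a* of these a year in every arm (an assumption; the protocol gives no rate), the ratio is (k + a)/(2 + a), where k is the number of scheduled contacts:

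| a | Minimal support (k = 3 to 5) | Nurse support (k = 5 to 9) |
|---|---|---|
| 1 | 1.3 to 2.0 | 2.0 to 3.3 |
| 2 | 1.3 to 1.8 | 1.8 to 2.8 |
| 4 | 1.2 to 1.5 | 1.5 to 2.2 |
| 6 | 1.1 to 1.4 | 1.4 to 1.9 |

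For example, at a = 4: (5 + 4)/(2 + 4) = 1.5 and (9 + 4)/(2 + 4) = 2.2.

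**3. From opportunities to recorded complications**

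Suppose each contact has a chance q that an existing problem is written down. The probability of at least one record in k scheduled contacts is 1 − (1 − q)^k:

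| q (assumed) | k = 2 | k = 3 | k = 5 | k = 9 |
|---|---|---|---|---|
| 0.05 | 0.10 | 0.14 | 0.23 | 0.37 |
| 0.1 | 0.19 | 0.27 | 0.41 | 0.61 |
| 0.2 | 0.36 | 0.49 | 0.67 | 0.87 |
| 0.5 | 0.75 | 0.88 | 0.97 | 1.00 |

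Adding 4 ordinary attendances at q = 0.1 gives 1 − 0.9^6 = 0.47 for control, and 1 − 0.9^9 = 0.61 to 1 − 0.9^13 = 0.75 for nurse support. The gap narrows but does not close. It is small when q is high, as it would be for a serious event that reaches the notes by any route, and largest in relative terms when q is low, as for minor complaints.

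**4. Time to return**

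Assume the same rate λ of unscheduled attendance in every arm. The median time to the first one is 52 × ln 2/λ weeks: 36, 18, 9 and 6 weeks at 1, 2, 4 and 6 a year. If scheduled visits were counted as returns, the median would be 2 weeks in both web arms and 26, 18, 9 and 6 weeks in control. If they are excluded, the arms agree. The arm difference therefore depends on a definition that the protocol leaves open.

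**The case against.** Several arguments on the other side have force.

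- **Returns can be separated.** The notes review also collects the reasons for returns, and nurses keep a tick-box log of the support they give. The data needed to set trial visits apart are therefore being gathered, and the definition could sit in an analysis plan or extraction form that is not at hand. This stands, and it reduces the question of returns to a clarification. A reader might infer that the schedule fixes time to return, or that these measures show the visit schedule and not harm. The protocol supports neither. It never says that trial visits count as returns, and it does not call time to return a safety measure. Even if they did count, control patients who attend early for other reasons would return before 6 months. Nor does a schedule create complications.
- **Some harm-related data are symmetric.** Table 1 lists liver function, ferritin and blood pressure at baseline, 6 and 12 months in all arms, and EQ-5D at the same points. Admissions and attendance also draw on nurse and GP documentation and patient self-report. This stands in part: the measurements are even-handed, but they cover only some possible harms, and the self-report is described for resource use, not complications.
- **The control visits are more than weighing.** The outcome measurement text and Table 1 put physiological measurements at the 6- and 12-month visits in every arm. This stands, so the argument rests on the number of contacts and not on what happens at those two visits.
- **The counts overstate the contrast.** Early nurse visits are offered, not guaranteed; nine is a conditional ceiling; ordinary attendances dilute the ratio. All of this stands.
- **Double costing is only a possibility.** Nothing in the economic analysis says that trial visits enter both as intervention and as service use. This stands.
- **The control arm is deliberately measured lightly.** The stated reason is that behavioural questions might prompt behaviour change. General health questions do not fall under that reason, and control patients already complete EQ-5D at 6 months.

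**Conclusion.** The concern holds as a risk of unequal ascertainment of complications. Practice notes are their only named source, and scheduled contacts after baseline are 2 in control, 3 face to face (5 with telephone) in minimal support, and 5 to 9 in nurse support. More recording is likely in the web arms. How much more cannot be derived from the protocol: it depends on ordinary attendance and on the chance of recording per contact, and neither is given. Under the assumed rates of 1 to 6 ordinary attendances a year, nurse support has 1.4 to 3.3 times the opportunities of control, always below the 2.5 to 4.5 from trial contacts alone at the corresponding number of visits.

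The primary outcome, weight, is not affected. The protocol specifies no formal test of complications, so what is at stake is how far any comparative statement on harm can be trusted. The handling of returns, consultation counts and visit costs needs only a clarifying line.

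**What to change.** Add an identical short set of questions on health problems and complications for all three arms to the existing 6- and 12-month data collection. Base any comparative statement on harm on these answers, together with admissions and notes entries from non-study attendances. This equalises the opportunity to report, although patients who know their allocation may still differ in what they choose to report.

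As a minor clarification under Notes review, flag protocol-scheduled contacts on the extraction form, so that returns, time to return and consultation counts exclude them and the economic analysis costs them once, as intervention.

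The cost is slightly longer data collection at two existing points and one extra column on the form. No new visits or staff are needed.

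### The flat 0.017 is stricter than three arms require, and 174 per group gives about 75% power under it, not 80%; Shaffer's step-down recovers power within the same 5% family-wise limit

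*Protocol*

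**What the plan says.** The Sample size section of the protocol sets out to "compare each of the intervention groups primarily with control but also with each other", which makes three pairwise comparisons. For weight, the primary outcome, "we allow for alpha=0.017 (i.e. 0.05/3) to minimise type I error". The remaining inputs are "For a standardised effect size of 0.33", described as "equivalent to 2-3 Kg difference assuming an SD of change of 6.5-7.5 Kg". The result is "80% power this requires 174 patients per group with complete data", or "654 patients in total allowing for 20% loss to follow-up", with a recruitment target of at least 660.

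Under Analyses, the primary analysis is "Repeated measures ANOVA for the principal continuous outcomes (i.e. weight) between groups", adjusted for the stratification variables. No stepwise, closed or gatekeeping procedure is named. The only multiplicity rule in the protocol is the 0.017 in the sample size paragraph. Sidedness is not stated.

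**The concern.** There are two linked problems.

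First, the stated power does not follow from the stated inputs. At 0.017 two-sided, 174 per group falls short of 80%.

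Second, the rule behind that shortfall is stricter than the design needs. With exactly three means, if two of the pairwise null hypotheses are true, the third must be true as well. So either all three are true, or at most one is. Once one null has been validly rejected, at most one true null can remain, and no further division of alpha is needed. A flat 0.05/3 ignores this.

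At stake is the chance of detecting the effect of each web arm against control, which the research objectives ask about separately. If both arms reach the planned effect, the chance of showing both is 62% under the flat rule and 76% to 78% under a procedure that uses this logical structure.

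**Working it through.** **Inputs (Sample size section).** d = 0.33; power 80%; alpha 0.017 (0.05/3) per comparison; 174 per group with complete data; 20% loss. Assumption: two-sided tests.

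**1. The protocol's own figure.** n per group = 2(z₁₋α/₂ + z₀.₈₀)² / d².
- Alpha 0.017: z = 2.387. 2 × (2.387 + 0.842)² / 0.1089 = 191.4, so 192.
- Exactly 0.05/3: z = 2.394. The same formula gives 192.3, so 193.
- Alpha 0.025 (0.05/2): z = 2.241. This gives 174.6, so 175.
- One-sided 0.017 gives 162.

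The stated 174 is therefore not reproduced at 0.017. It lies close to what two comparisons (0.05/2) would need.

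The dropout step is right: 174/0.8 = 217.5, rounded up to 218, and 218 × 3 = 654. With 192 per group it would be 192/0.8 = 240, and 240 × 3 = 720.

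**2. Power at 174 under the flat rule.** Φ(d√(n/2) − z) = Φ(0.33 × √87 − 2.387) = Φ(3.078 − 2.387) = Φ(0.691) = 75.5% (75.1% with the t distribution). The 176 per arm expected from 660 (220 × 0.8) gives 76.1%.

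**3. Two procedures that control family-wise error at 5% with three arms.**
- Shaffer's step-down: test the smallest p at 0.05/3; if it is significant, test the other two at 0.05. Any p below 0.05/3 is still rejected, so nothing that Bonferroni rejects is lost.
- Closed global test: a between-group test on 2 df at 0.05; if significant, each pair at 0.05. Every intersection of two pairwise nulls is the global null, so this is a full closed procedure.

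**4. Power at 174 per arm.** Simulation with normal outcomes, pooled SD and two-sided t tests. Effects are in SD units against control.

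| Effects of the two web arms | Power for | Flat 0.05/3 | Shaffer | Closed global |
|---|---|---|---|---|
| 0.33, 0.33 | each arm v control | 75% | 82% | 84% |
| 0.33, 0.33 | both v control | 62% | 76% | 78% |
| 0.33, 0 | effective arm v control | 75% | 82% | 84% |
| 0.33, 0.165 | stronger arm v control | 75% | 77% | 78% |
| 0.33, 0.165 | weaker arm v control | 20% | 32% | 33% |
| 0.33, 0.25 | stronger arm v control | 75% | 78% | 80% |

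**5. Error rates.**
- All three arms equal: family-wise error is 4.4% for the flat rule and for Shaffer, and 5.0% for the closed global test.
- One pair equal and the third arm far away: error for that pair is 1.7% for the flat rule and 5.0% for both alternatives.

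**6. Does either alternative ever lose a Bonferroni rejection?** Shaffer: never, by construction and in the simulation. Closed global test: in about 0.2% to 0.5% of trials. When the third arm lies midway, the global statistic equals z² for the extreme pair, so |z| must exceed √5.991 = 2.448, against 2.394 for Bonferroni.

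**The case against.** The strongest reply is that 0.017 is a planning allowance. It stands under Sample size, the Analyses section fixes no testing level, and an SAP that is not shown could name a stepwise procedure. That is possible. But the protocol states the alpha rule, gives its purpose, and derives the sample size and power claim from it, so the rule and the figure can be judged as written.

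The second reply is that Bonferroni is valid and simple, gives intervals that match the decisions, and suits an aim of minimising type I error. All of this stands. It is why the point is one of efficiency and not of validity. Error for a single truly null pair does rise under the alternatives, so the gain is not free, although family-wise error stays within 5%.

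The third reply is that the shortfall comes from the wrong 174, because Bonferroni with 192 per group would deliver 80%. That is correct. Changing the test does not make 174 the right answer to the protocol's own calculation, and the power statement needs correcting either way. The step-down advantage does not depend on that error, however: at any sample size Shaffer rejects at least as much as the flat rule.

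A reader might also infer that a closed test restores 80% in general. The protocol gives no ground for assuming equal effects in the two web arms. It describes the minimal-support arm as very brief, so an intermediate effect there is plausible, and the stronger arm then stays at 77% to 80%. Nor does the closed global test dominate Bonferroni outright, as step 6 shows.

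**Conclusion.** The point holds as a recommended change. On the protocol's inputs, two-sided, 174 per group gives about 75% power at 0.017, and 80% needs about 192 per group. The flat rule is valid but needlessly strict for three arms.

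At 174 per group, Shaffer gives 82% and the closed global test 84% per comparison with control, if both web arms reach 0.33 or if one does and the other equals control. For the stronger arm this falls to 77% to 80% if the other has an effect between 0.165 and 0.25. These are powers per comparison, as in the protocol's own calculation; the power to show both arms better than control stays below 80% even in the best case (76% to 78%).

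The figures rest on two-sided testing, equal arms, normal outcomes, and a single standardised difference of 0.33 per contrast. The gain from the repeated measures structure was not modelled. The documents do not support the stronger readings that the protocol's type I error control is faulty, or that the change costs nothing in type I error.

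**What to change.** Add to the primary analysis: *The three pairwise between-group contrasts for weight, estimated from the repeated measures model, will be tested two-sided by Shaffer's step-down: the smallest p-value at 0.05/3 and, if it is significant, the other two at 0.05. Family-wise error is at most 5%.*

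A global between-group test at 0.05 followed by each pair at 0.05 is an acceptable alternative. It is slightly more powerful on average but does not strictly dominate Bonferroni. In either case the contrasts should come from the model already planned, so that the primary analysis is not changed to a single 12-month comparison.

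Restate the power for 174 per group: about 75% with flat 0.017; 82% (Shaffer) or 84% (closed global test) per comparison with control if both web arms reach 0.33, or if one does and the other equals control; 77% to 80% for the stronger arm if the other is intermediate. If flat 0.017 is kept, 80% needs about 192 per group, or 720 in total with 20% loss.

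The change is one of wording and needs no extra patients. Unadjusted 95% intervals will no longer match the decisions one-to-one, which should be said when they are reported. Error for a single truly null pair rises from 1.7% to at most 5%.

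### At the stated alpha of 0.017 and effect of 0.33, 174 per group gives about 75% pairwise power, not 80%; the stated inputs need 192 to 193 per group

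*Protocol*

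**What the plan says.** The Sample size paragraph of the protocol gives the calculation in full.

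- Comparisons: "We wish to compare each of the intervention groups primarily with control but also with each other". With three arms, that makes three pairwise comparisons.
- Error rate: "we allow for alpha=0.017 (i.e. 0.05/3) to minimise type I error".
- Target effect: "For a standardised effect size of 0.33", glossed as "equivalent to 2-3 Kg difference assuming an SD of change of 6.5-7.5 Kg".
- Result: "80% power this requires 174 patients per group with complete data, or 654 patients in total allowing for 20% loss to follow-up".
- Recruitment: "we will aim to recruit a minimum of 660 patients".

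The paragraph does not say whether the tests are one- or two-sided. It gives no correlation or other variance reduction. The Analyses section names a repeated measures ANOVA that controls for the stratification variables.

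**The concern.** Alpha, effect size and power are all stated, and 174 is presented as their result, so the sentence can be checked on its own terms without a statistical analysis plan. The usual formula for comparing two means gives a figure about 10% larger. Either the number of patients or the stated power is therefore wrong for the stated alpha.

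This paragraph is the protocol's only justification of the trial's size on its primary outcome, and the discrepancy flatters the design. For each comparison, the chance of missing a true difference of 0.33 SD is about 25% rather than the stated 20%. The kilogram gloss adds to this. A reader could take it as 80% power across the whole range from 2 to 3 kg, which the standardised effect does not cover.

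**Working it through.** **Inputs** (all from the Sample size paragraph): alpha 0.017 per comparison, standardised difference d = 0.33, power 80%, equal groups, 20% loss, at least 660 recruited. Assumed: two-sided tests.

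**1. The loss-to-follow-up step reproduces.** 174/0.8 = 217.5, rounded up to 218 per group, and 3 × 218 = 654. The problem lies in the 174 itself.

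**2. Patients per group from the stated inputs.** n = 2(z₁₋α/₂ + z₀.₈₀)²/d².

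- α = 0.017: 2(2.387 + 0.842)²/0.1089 = 191.4, so 192 (193 with the t distribution).
- α = 0.05/3 unrounded: 192.3, so 193 (194 with t).
- Recruited with 20% loss: 3 × 192/0.8 = 720; 3 × 193/0.8 = 723.75, so 724.

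**3. Power at the planned size.** Power ≈ Φ(d√(n/2) − z₁₋α/₂).

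- n = 174: Φ(0.33 × √87 − 2.387) = Φ(3.078 − 2.387) = Φ(0.691) = 75.5% (75.1% with t).
- 660 recruited with 20% loss: 660 × 0.8/3 = 176 per group; Φ(0.33 × √88 − 2.387) = Φ(3.096 − 2.387) = Φ(0.709) = 76.1% (75.7% with t).

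**4. Effect detectable with 80% power at 176 per group.** √(2/176) × (2.387 + 0.842) = 0.344 (0.346 with t), so about 0.345 SD. In kilograms, 0.345 × 6.5 = 2.2 and 0.345 × 7.5 = 2.6.

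**5. Other routes to 174.**

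- One-sided 0.017 gives 162 per group.
- An effect of 1/3 in place of 0.33 gives 188.
- Two-sided 0.025 gives 2(2.241 + 0.842)²/0.1089 = 174.6, which is close (175 if rounded up).
- An omnibus three-group F test at 0.017, with one arm 0.33 SD from the other two, reaches 79.8% power at 173 per group and 80.1% at 174. So 174 is the smallest size that passes.
- A covariate correlation of √(1 − 174/191.4) = 0.30 would reduce the requirement to 174.

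The 0.025 route changes the alpha, the F-test route changes the hypothesis tested, and the last needs a correlation that the protocol does not give.

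**6. Kilogram gloss.** 0.33 × 6.5 = 2.1 kg and 0.33 × 7.5 = 2.5 kg. In the other direction, 2/7.5 = 0.27 and 3/6.5 = 0.46, so 2 to 3 kg over the quoted SDs spans effects well to either side of 0.33.

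**The case against.** The best defence is that 174 may be a correct answer to a different question. The F-test route in step 5 gives exactly 174 at the protocol's own alpha, and the protocol names an ANOVA as its primary analysis. This stands as a possible origin of the figure. It does not rescue the sentence, because the division of 0.05 by three is made for pairwise comparisons, the omnibus calculation is not described, and it does not deliver 80% power for any pair at 0.017.

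For the same reason, a reader might infer that the trial was sized at alpha 0.025, that is, for two comparisons. The documents do not support this as fact. The protocol never mentions 0.025, that alpha rounds up to 175, and the F test fits at least as well.

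A second defence is that adjustment and repeated measures would recover the power. A correlation of about 0.30 would do it. None is stated, and the SD quoted is already that of change.

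Third, 660 is a minimum. The recruitment section plans 15 to 20 patients in each of up to 44 practices, or 660 to 880 if all 44 take part, so about 720 lies within capacity. At 660, a loss of about 12 to 13% would also leave 192 to 193 per group. Both points are fair and limit the consequence, but the paragraph itself assumes 20% loss.

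Finally, a reader might infer from the 2 to 3 kg range that power is near one half. That is true only of 2 kg with an SD of 7.5 kg (54% at 174 per group). The opposite corner, 3 kg with an SD of 6.5 kg, has 97%. The protocol powers for 0.33 SD and claims nothing at 0.27, so neither corner describes the design.

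**Conclusion.** The statement is wrong as written. For pairwise two-sided comparisons at 0.017 and an effect of 0.33 SD, 80% power needs 192 to 193 per group; 174 gives about 75%, and 660 recruited with 20% loss gives about 76%. The result rests on the two-sided assumption and on no variance reduction beyond the use of an SD of change. The one-sided reading does not reproduce 174 either. How 174 arose is unknown, and the finding does not depend on it.

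The size is modest: 4 to 5 points of power, 18 to 19 completers per group, or a detectable effect of about 0.345 rather than 0.33 SD (roughly 0.1 kg). A reader might conclude that the trial is seriously underpowered or must recruit more. The figures do not support that. The type I error rate, the tests and the estimates are unaffected. This is a correction to the sample-size statement, not a redesign.

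**What to change.** Keep the minimum of 660 and rewrite the Sample size paragraph along these lines: with 660 recruited and 20% loss, 176 per group are analysed; at a two-sided alpha of 0.017 per pairwise comparison, power is about 76% for a standardised difference of 0.33 (2.1 to 2.5 kg for an SD of change of 6.5 to 7.5 kg), or 80% for about 0.345 (2.2 to 2.6 kg). State the sidedness, and replace the 2 to 3 kg range with the one that matches the effect quoted.

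If 174 came from an omnibus calculation or assumed a correlation, the sponsor should say so and still give the pairwise power.

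The cost is one reworded paragraph and a slightly less favourable stated power. No extra patients are required.
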